8.1 Sample size calculations

The study in the current form is a randomized feasibility study where the main objective is to test if the intervention and study design is feasible enough for a full size study randomized controlled trial. We will therefore only include 40 participants in this phase of the study.

A full size randomized controlled trial will no doubt require a larger sample size if we were to expect an effect to be found. In a meta-analysis of fairly similar interventional studies Lawrence et al. found that the weighted means of the systolic blood pressure were 132.5 (SD 18.3; n=682) mmHg in the intervention groups and 136.2 (SD 21.5; n=725) in the control groups, respectively, and with a mean difference of 4.21 mmHg (95%CI 2.18-6.24).

Using the estimates from Lawrence et al. we can estimate the sample size needed with the method for comparing two means as reported by Kirkwood & Stern ((12)p 420) with the following assumptions:

- An equal number of participants are allocated to the two groups
- The blood pressure values are approximately normally distributed
- An alpha of 5 percent (probability of Type I error) and a beta of 20 percent (probability of Type II error)

From this it is estimated that we will need a sample-size of 596 (298 in each group), not adjusting for losses to follow-up.

8.2 Descriptive analysis

The recruitment, randomization, allocation, and follow-up will be described in a flow-chart stating how many participants were available at each step. We will report characteristics of patients, who are either: excluded, non-consenting, or lost to follow-up in as much detail as possible.

To ensure the external validity of the study we will thoroughly report the characteristics of the participants, both collectively and by treatment group. Participant characteristics will be reported in a table with columns for both treatment groups and a p-value for the differences between treatment groups. The p-values will be calculated using student's test for continuous variables and chi-squared test or fisher's exact test for categorical variables.

8.3 Statistical analysis

Hypothesis testing for the secondary outcome (systolic blood pressure) will be done as intention-to-treat (including all participants allocated) using a paired t-test comparing baseline systolic blood pressure with systolic blood pressure measured after 12 weeks. Results will be reported as mean difference of changes with 95 percent confidence intervals.

Tertiary outcome measures will be analyzed as intention-to-treat using unpaired student t-test for continuous variables and either chi-squared test or fisher's exact test for categorical variables. Treatment allocation will be blinded to the investigator.

Statistical analyses will be done in R 3.3.1/R Studio 0.99. A significance level of 5 percent will be considered statistically significant.

9 Validity and bias

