1.3.4 Statistical analyses

Student t-test will be used as significance test for differences in blood pressure between the treatment groups.

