7.4 Data control and editing

To avoid extreme values the eCRF will have set ranges of plausible values for numerical variables and it will not be possible to enter values outside the ranges.

Before data analysis the data will be checked for missing values. If values are missing we will attempt to reconstruct the information from medical records or by contacting the participant.

The data will be tested for abnormal values by the primary investigator:

Dates – The dates of symptom onset, admission, and discharge will be compared to ensure the differences are not unrealistically bigger than expected, and by testing if any dates are outside the study period.

Categorical variables – Will be checked for missing or illegal values with frequency distributions

Numerical variables – Will be checked for extreme/illegal values with summary statistics and by histograms/boxplots

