9.1 Data sources

Administrative information (e.g. time of admission/discharge) is recorded real-time and is therefore reasonably reliable. Medical information (e.g. comorbidities) should be confirmed by clinical or para-clinical tests if possible. All information obtained from the medical records will be verified with the participant to sort out flawed information.

The validity of information obtained from participant interviews can be affected in different ways. There might be problems with the internal validity of the questions used, which means that the

answers that are given might not represent what we think they are. Also participants might not be completely honest in their answers and we do not always have ways to validate them.

The biggest threat to the validity of the study will be missing data; especially due to participants been lost to follow-up. Participants will not always be missing at random. They might have some commonality, which will result in an uneven representation.

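### Section 8.3 labels the blood pressure analysis intention-to-treat on everyone allocated, but its t-test uses only participants with a 12-week reading, and nothing covers values that stay missing.

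*Combined protocol and SAP*

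**What the plan says.** **Analysis set and test.** Section 8.3 says SBP will be analysed as "intention-to-treat (including all participants allocated"), "using a paired t-test comparing baseline systolic blood pressure with systolic blood pressure measured after 12 weeks". The synopsis, section 1.3.4, gives a different test: "Student t-test will be used as significance test for differences in blood pressure between the treatment groups". Results are to be given as a mean difference of changes with a 95% confidence interval.

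**Expected missing data.** Section 9.1 states: "The biggest threat to the validity of the study will be missing data; especially due to participants been lost to follow-up". It adds: "Participants will not always be missing at random". Section 1.5 also names participation and retention as the study's hardest task.

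**Handling.** Section 7.4 says: "If values are missing we will attempt to reconstruct the information from medical records or by contacting the participant". Section 8.2 promises a flow-chart and a description of those lost to follow-up. No section gives an imputation rule, a model that uses incomplete records, or a sensitivity analysis for missing SBP. Section 8.1 assumes no dropout rate.

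**Measurement.** Section 7.1.1 defines the 12-week reading: seated, after ten minutes' rest, the median of three. Section 7.1.2 lists systolic pressure among the vital signs recorded before randomisation.

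**The concern.** An intention-to-treat label tells the reader that everyone randomised contributes to the comparison. A t-test that needs a 12-week value cannot deliver that once anyone is lost, so the stated set and the stated method conflict. This goes beyond missing detail: two statements in the same sentence cannot both be carried out.

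Testing the effect on blood pressure is one of the two aims in section 3.2, section 8.3 sets a 5% significance level, and section 11.2 commits to publication whatever the result. A completer result could therefore be published as intention-to-treat. Retention may also differ by arm, because only the counselling arm has the 3-4 follow-up sessions of section 5. If those lost would have changed differently from those who stay, and more so in one arm, the between-arm difference is biased.

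The retrieval step in section 7.4 adds a second risk. As written, it could bring in a 12-week value that was not measured as section 7.1.1 requires.

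**Working it through.** The plan gives no figure for dropout or bias, so there is none to reproduce. The sample size of 596 in section 8.1 is for a future trial and is not an input here.

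**1. Who enters the test.**
- Paired t-test (8.3): needs baseline and 12-week SBP.
- Between-group t-test (1.3.4): needs 12-week SBP.
- Retrieval (7.4): may reduce the number missing, but leaves out whoever stays missing.
- Flow-chart and description of losses (8.2): reports who is missing, but does not change who is tested.

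With 40 participants and an assumed dropout of 10%, 20% or 30%, the test uses 36, 32 or 28 people, not 40. The log transformation considered in section 7.5 would not alter this.

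**2. Size of the bias.** In one arm let *p* be the share lost, *C* the mean SBP change in completers, and *D* the mean change the lost participants would have had.

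- Mean change for all allocated = (1 − p)·C + p·D
- Completer mean minus that = p·(C − D) = p·g, where g is the gap in *change*
- Bias of the between-arm difference = p₁g₁ − p₂g₂ (arms 1 and 2)

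A stable difference in SBP level between dropouts and completers cancels in change scores, so only the gap in change counts. Equal loss with an equal gap in both arms gives zero. If the gap exists in one arm only, the bias is p·g:

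| Dropout (assumed) | Gap 5 mmHg (assumed) | Gap 10 mmHg (assumed) |
|---|---|---|
| 10% | 0.10 × 5 = 0.5 | 0.10 × 10 = 1.0 |
| 20% | 0.20 × 5 = 1.0 | 0.20 × 10 = 2.0 |
| 30% | 0.30 × 5 = 1.5 | 0.30 × 10 = 3.0 |

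The sign follows the sign of the gap and the arm in which it occurs.

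**3. Sampling error for comparison.** Section 8.1 quotes SDs of 18.3 and 21.5 mmHg from a meta-analysis. Their root mean square is √[(18.3² + 21.5²)/2] = 19.96. Assume equal arms with n analysed per arm:

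- Half-width of the 95% CI = t(0.975; 2n − 2) × 19.96 × √(2/n)
- n = 20: 12.8 mmHg
- n = 18: 13.5 mmHg
- n = 16: 14.4 mmHg
- n = 14: 15.5 mmHg

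These SDs describe SBP level. The documents give no SD of change, so the half-widths are only a yardstick. Against them, a bias of 0.5-3 mmHg is small.

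**The case against.** The strongest case on the other side is about stakes. This is a 40-patient feasibility trial. SBP is secondary in sections 7.1.1 and 8.3 (although 1.3.2 and 7.5 call it primary), and section 1.4 carries forward the participation rate and the SBP variance, not the effect. Section 8.2 already shows the reader how many were lost. One sentence naming the set as complete cases would remove the contradiction, and with a single follow-up visit a model moves the estimate little. All of this stands, and it limits the weight of the point. It does not reconcile the set with the test or say what happens to values that stay missing.

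Four stronger readings are tempting, and the documents do not support them.

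- *The completer result will favour the intervention.* No document gives a direction. Losing unmotivated patients could favour it. Losing patients with high baseline SBP, who might have fallen most through regression to the mean, could work against it.
- *The plan says losses will be informative.* Section 9.1 says only that data will not always be missing at random, and mentions neither arm nor direction.
- *Section 7.4 would replace the 12-week SBP with a routine reading.* It is a general data-cleaning step. It could allow that, but it does not say so.
- *The bias is a large share of the 4.21 mmHg effect.* That figure comes from a meta-analysis and is used in section 8.1 for a future trial. Both inputs to the bias are assumed, so percentages of it would suggest more than is known.

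That a paired test is not a between-arm comparison, and so disagrees with section 1.3.4, is a separate matter. Either test drops the same people for want of a 12-week value.

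**Conclusion.** The point holds as a mismatch between label and method, together with an unfilled gap. As written, section 8.3 yields a complete-case analysis called intention-to-treat whenever a 12-week SBP stays missing, and no planned analysis tests the non-random loss that section 9.1 anticipates.

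The numerical effect is uncertain and probably modest. It is 0.5-3 mmHg in either direction, if dropout is 10-30%, the gap in SBP change is 5-10 mmHg, and the gap occurs in one arm only. Similar losses in both arms would largely cancel. Sampling error with 40 patients is several times larger, so this bias is unlikely to decide the result. The reason to correct it is that the published label should be true, and that a feasibility trial is the right place to try out missing-data handling before a full trial. It should be changed, but it does not threaten the feasibility aim.

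**What to change.** Amend section 8.3 as follows.

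1. Analyse all randomised participants with a baseline SBP in their allocated arm, using a model for baseline and 12-week SBP with a common baseline mean, and report the between-arm difference at 12 weeks. The baseline value is already collected (section 7.1.2).
2. Add a short sensitivity analysis that shifts missing 12-week values from the model's prediction by stated amounts, for example 5 and 10 mmHg higher, in the intervention arm only and then in both arms. With 4 of 20 missing in the intervention arm, these shifts move the difference by 4/20 × 5 = 1 mmHg and 4/20 × 10 = 2 mmHg.
3. Accept as a 12-week SBP only a reading taken as section 7.1.1 describes, and say in section 7.4 that retrieval does not override this.
4. Report the number of missing 12-week SBP values by arm, and call any t-test on completers a complete-case analysis.

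The cost is SAP wording and slightly more analysis. With one follow-up visit, item 1 alone will move the estimate little, so item 2 is what examines non-random loss. Its result may look less favourable to the intervention.

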1.3.2 Exposures and outcomes of interest

Participation rate and adherence to the treatment program will be the primary outcome measures of feasibility. Systolic blood pressure will be the primary outcome measure of effect.

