3.3 Hypothesis

The hypothesis of the study is that early client-centred patient counselling with repeated follow-up sessions after discharge can reduce the blood pressure through smoking cessation, physical activity, and improved adherence to preventive medication in patients with minor stroke and transient ischemic attacks compared to simple encouragement to lifestyle change.

4 Populations

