4.3 Study population

We will include patients with acute minor stroke or TIA admitted to the Department of Neurology at Nordsjællands Hospital (n=40).

Inclusion criteria

- Male or female, age \geq 18 years old
- TIA (ICD-10 G45.9) or stroke (ICD-10 I61, I63, I64) with a Scandinavian Stroke Scale of 45-58.
Diagnosis must be confirmed by a neurologist
- Able to give a valid written consent

Exclusion criteria

- Severe barriers to communication
- Not able to use a telephone
- Severe disability prior to the stroke (WHO Performance Status >2; mobilised less than 50 % of the day)
- Active abuse of alcohol or narcotics
- Severe psychiatric illness (affective disease, dementia, schizophrenia, anxiety)

5 Study design

The study will be a parallel group randomized controlled feasibility trial. Participants will be randomly allocated to either usual care or a counselling intervention, with follow-up sessions post-discharge with 3-4 weeks intervals in 12 weeks.

Intervention

Participants in the intervention group will receive targeted counselling in lifestyle changes focusing on smoking cessation, everyday physical activity, and adherence to preventive medication. The primary aim of the initial counselling session will be to assess the participant's intentions and willingness to change behaviour, and to support the participant in establishing realistic goals. The participants will be encouraged to bring a relative or close friend to the initial counselling session, who can be a support for the participant after the discharge.

Ahead of the initial counselling session we will do a detailed assessment of the participant's lifestyle and physical condition; including an assessment of lung function and oxygen uptake.

After the participants are discharged from the hospital we will do 3-4 follow up counselling sessions. The aim of these sessions will be to re-evaluate the previous goals or to re-assess the participant's willingness to change if the participant continues to be ambivalent about lifestyle changes.

The participant's level of physical activity will be monitored from the discharge to the last follow up after 12 weeks. The participant will be handed out an activity tracker from the hospital which will record all movement day and night.

Usual care

Participants in the control group will receive the standard care, which include a review of prescribed medication, and both verbal and written encouragement of a healthy lifestyle.

[figure not shown]

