7.1 Variables

7.1.1 Outcome variables

Measures of feasibility

The primary outcome measure will be the rate of participation in the study; measured as:

- 1) the proportion of patients eligible for the study out of all patients with stroke admitted to the Department of Neurology,
- 2) the proportion of patients accepting to participate in the study, and
- 3) the degree of adherence to the intervention (proportion of attendance in follow-up sessions)

Aside from participation we will evaluate the participants' satisfaction with the overall intervention and single parts of the intervention.

Variable	Measure	Type/scale	Source
Admissions	Number of patients admitted in the study period	Continuous	
Eligibility	Number of patients who would be candidates for participation	Continuous	
Recruitment	Number of participants recruited	Continuous	
Adherence	Number of participants completing the treatment Degree of participation	Continuous	
Satisfaction	Five level Likert Scale	Ordinal	

Secondary outcome

Measure of effect

The secondary outcome measure will be arterial blood pressure measured 12 weeks after the start of the intervention. The arterial blood pressure will be measured as a continuous variable in mmHg. The participant should be sitting still and resting for ten minutes before the measurement. To avoid extreme values the measurement will be repeated three times with a few minutes apart and the median value will be used for the statistical analysis.

This outcome measure was chosen because hypertension is the most significant risk factor for stroke and TIA (5) and because previous studies have found that it might be possible to lower the blood pressure through lifestyle interventions (8).

Tertiary outcomes

Tertiary outcomes after 12 weeks will include:

Variable	Measure	Type/scale	Source
Changes in behavior			
Smoking	Daily; weekly; Rarely; Former; Never smoked	Categorical	B
Physical activity	Questionnaire	Ordinal	B
Adherence to medication	Questionnaire	Continuous	B
Anthropometric measures			
Body weight	Measured (kg)	Continuous	C
Height	Measured (cm)	Continuous	C
Waist + hip circumference	Measured (cm)	Continuous	C
Patient reported outcomes			
Fatigue	Questionnaire		B
Self-rated health	Two item questionnaire	Categorical	B

Secondary outcomes after one year will include:

Variable	Measure	Type/scale	Source
New stroke/TIA	Event + days till event	Categorical/time	A
Cardiac admission	Event + days till event	Categorical/time	A

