The study will be conducted in accordance with the Helsinki-declaration (13); including respect for the participants' autonomy and right to informed consent. The participants will be informed that the participation in the study as a whole and the single parts of it will be voluntary and that they have the right to decline participation at any time and without giving a cause for their refusal.

The inconveniences of participating will be minor and we are convinced that the potential benefits will outweigh the drawbacks. The main inconveniences of the study will be withdrawing symptoms, associated with smoking cessation, and muscle soreness from increased physical activity. Generally this will be both minor and transient.

The use of a control group as a comparison is necessary if we wish to find evidence of the hypothesised effect of the treatment and gain a better understanding of the variation in the outcome measures. It will also be necessary to test the feasibility of the randomization process prior to the design of a full scale randomized controlled trial. The treatment of the participants in the control group will at no point be inferior to the treatment of non-participants.

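### The blood pressure test in 8.3 compares baseline with 12 weeks, not the two arms; it contradicts 1.3.4 and cannot test the hypothesis in 3.3

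*Combined protocol and SAP*

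**What the plan says.** Section 8.3 sets the hypothesis test for SBP, by intention to treat, "using a paired t-test comparing baseline systolic blood pressure with systolic blood pressure measured after 12 weeks". No treatment group appears in that sentence. The next one says: "Results will be reported as mean difference of changes with 95 percent confidence intervals". For continuous tertiary outcomes the same section specifies an unpaired t-test.

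Other sections point to a comparison of the arms:

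- 1.3.4 (summary): "Student t-test will be used as significance test for differences in blood pressure between the treatment groups".
- 3.3 expects counselling to lower blood pressure "compared to simple encouragement to lifestyle change".
- 11 (Ethical considerations): "The use of a control group as a comparison is necessary if we wish to find evidence of the hypothesised effect of the treatment".
- 8.1 sizes the future trial by a comparison of two means.

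The status of SBP varies. Section 7.1.1 has "The secondary outcome measure will be arterial blood pressure measured 12 weeks after the start of the intervention", and 8.3 also calls it secondary. Section 1.3.2 says "Systolic blood pressure will be the primary outcome measure of effect", and 7.5 calls it the primary outcome.

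**The concern.** A paired test of two time points asks whether SBP changed. It does not ask whether it changed more with counselling than with usual care. Section 8.3 does not say whether the test is pooled over everyone randomised or run within each arm, and neither version tests the difference between arms. Pooling discards the randomisation. Running the test in each arm invites the inference that significance in one arm and not in the other shows an effect.

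What is at stake is the named test and its p-value. If SBP falls in both arms for reasons unrelated to counselling, the paired test can be significant when counselling does nothing. The documents do not state such a fall, but they make it plausible. Patients are approached in hospital, usually within the first few days (6.1). Most are prescribed antithrombotic, blood-pressure-lowering or lipid-lowering drugs (section 2). Control patients receive "standard care, which include a review of prescribed medication" (section 5, Usual care).

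**Working it through.** **1. The sections side by side**

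| Section | Contrast | Null hypothesis |
|---|---|---|
| 8.3, named test | baseline v. 12 weeks | no change over time |
| 8.3, reported result | difference of changes, groups not named | no test attached |
| 1.3.4 | between treatment groups | no difference between arms |
| 3.3 | counselling v. simple encouragement | no difference between arms |
| 8.1 | two means | no difference between arms |

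**2. The plan's own figure is a between-arm calculation.** Section 8.1 gives 298 per group (596 in total). With a difference of 4.21 mmHg, SD 18.3 in both arms, two-sided 5% and 80% power:

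n = (1.960 + 0.842)² × 2 × 18.3² / 4.21² = 7.849 × 669.78 / 17.724 = 296.6 per group.

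The t-distribution version gives 297.6, which rounds up to 298. The stated figure therefore reproduces as a two-sample comparison, and the paired test in 8.3 is the odd one out.

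**3. What the paired test does when there is no treatment effect.** Inputs:

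- SD 18.3 and 21.5 mmHg (8.1), each taken to apply at both visits.
- 40 participants (8.1). A split of 20 per arm is assumed; the equal allocation in 8.1 belongs to the future trial.
- No dropout (assumed).
- Baseline-to-12-week correlation r of 0.3 to 0.7 (assumed; not in the documents).
- The same mean fall in both arms, 5 or 10 mmHg (assumed).

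SD of change = SD × √(2(1 − r)). The noncentrality is fall / (SD of change / √n), and the rejection probability comes from the noncentral t with n − 1 df. Example: SD 18.3, r = 0.5 gives an SD of change of 18.3. For a 10 mmHg fall and n = 20, the noncentrality is 10 / (18.3/√20) = 2.44 and the rejection probability is 0.640.

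| SD | r | 10 mmHg, n = 20 | 10 mmHg, n = 40 | 5 mmHg, n = 20 | 5 mmHg, n = 40 |
|---|---|---|---|---|---|
| 18.3 | 0.3 | 0.500 | 0.813 | 0.165 | 0.297 |
| 18.3 | 0.5 | 0.640 | 0.921 | 0.213 | 0.392 |
| 18.3 | 0.7 | 0.849 | 0.992 | 0.322 | 0.585 |
| 21.5 | 0.3 | 0.386 | 0.679 | 0.133 | 0.228 |
| 21.5 | 0.5 | 0.506 | 0.818 | 0.167 | 0.300 |
| 21.5 | 0.7 | 0.722 | 0.959 | 0.247 | 0.457 |

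For smaller falls the problem shrinks: 2 mmHg gives 6–9% (n = 20) and 8–14% (n = 40), and 3 mmHg gives 8–15% and 11–26%.

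If the test is run separately in each arm with rejection probability p, the misleading pattern (significant with counselling, not with usual care) has probability p(1 − p). That is 13–25% for a 10 mmHg fall and 12–22% for 5 mmHg.

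**4. A between-arm test under the same conditions.** A common fall cancels from the difference in mean change, so the error rate stays nominal. Simulation of 40,000 trials per setting with a 10 mmHg common fall gave 4.9–5.2%, both for the unpaired t-test on changes and for ANCOVA.

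**5. What a between-arm analysis can deliver at 20 per arm.** Half-width of the 95% CI = t × SD* × √(2/20). SD* is SD for final values (38 df), SD√(2(1 − r)) for changes (38 df) and SD√(1 − r²) for ANCOVA (37 df).

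| Analysis | Half-width, mmHg | Power for 4.21 mmHg |
|---|---|---|
| Final values | 11.7–13.8 | 9–11% |
| Change scores | 9.1–16.3 | 8–15% |
| ANCOVA | 8.4–13.1 | 10–17% |

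Relative to final values, the variance is 0.91, 0.75 and 0.51 for ANCOVA and 1.40, 1.00 and 0.60 for change scores, at r = 0.3, 0.5 and 0.7.

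**The case against.** The strongest reply is that a between-arm contrast was intended and one phrase is wrong. A difference of changes, analysed by intention to treat, mainly makes sense for randomised arms, and 1.3.4, 3.3 and 8.1 all point the same way. Paired analyses in each arm would also supply each mean change and its standard error, from which the difference and its CI follow by subtraction.

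This is probably right about intent, but it does not repair the text. The sentence on reporting describes an estimate, names no groups and leaves the named test in place. Subtracting the arm-specific results would be a further analysis that 8.3 does not specify. Since 8.3 calls for an unpaired test for tertiary outcomes, an analyst following it literally would run the paired one for SBP.

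Two further points limit the concern:

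- The percentages depend on an assumed common fall and correlation. The drugs listed in section 2 are not all antihypertensives, and a medication review need not change treatment. The figures illustrate a mechanism and do not forecast this trial.
- Feasibility is the main objective (8.1), section 1.4 expects planning estimates, and no progression decision is tied to the SBP p-value. Even so, 1.1 and 3.2 make testing the effect on blood pressure an objective, and 8.3 sets a 5% significance level.

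**Conclusion.** The concern holds. The SBP test named in 8.3 contradicts 1.3.4 and cannot test the hypothesis in 3.3; this follows from the text and needs no assumption. The size of the harm does rest on assumptions. With no treatment effect, the SDs in 8.1, a correlation of 0.3 to 0.7, 20 per arm and no dropout, a common fall of 5 to 10 mmHg makes the paired test significant in 13–85% of trials in a single arm and 23–99% pooled, against about 5% for a between-arm test. A correctly computed between-arm CI would not be misled. It will be wide at this sample size, so the interval and not the p-value is the useful result. This should be fixed before analysis. The feasibility purpose and the mainly secondary status of SBP keep it from being more serious.

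**What to change.** In 8.3, replace the paired t-test with one between-arm analysis, for example: *The difference in 12-week SBP between intervention and usual care will be estimated by ANCOVA with treatment group and baseline SBP as covariates, and reported in mmHg with a 95% CI.* An unpaired t-test on change scores would also cure the error; ANCOVA is preferred for its precision. Name the same analysis in 1.3.4.

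Two details should be settled in the same edit:

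- State which baseline reading is used. Section 7.1.2 lists SBP only as a component of the Early Warning Score, while the ten-minute rest and the median of three readings are described in 7.1.1 for the 12-week outcome.
- Align 7.5, which tentatively suggests a log transformation, with an estimate reported in mmHg.

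The cost is wording only: no extra patients, and one degree of freedom for the covariate. If baseline and 12-week SBP are measured differently, the gain in precision may shrink, but the randomised comparison is not biased.
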